#### 8.1.3. Main Analysis – Output

The following information will be summarized:

- Number and percentage of patients with 0 / 1 / 2 / 3 or more events
- Estimate of mean and SD of the incidence rate by the simple estimator.

The following steps will be applied for the simple estimator:

1. For each patient calculate the observation period (see [Section 6.2.20](#))
2. The number of patient years will be calculated by summing the total patient days and dividing by 365.

This document is confidential.

3. An estimate of the mean (simple estimator) of acute serious bacterial infection rate for KIG10 will be obtained by dividing the total number of acute serious bacterial infections by the total number of patient years.
4. An estimate of the SD will be produced

- Estimate and 1-sided 99% upper confidence limit of the incidence rate from the Poisson model.

CCI

This document is confidential.

CCI

This document is confidential.

## 8.2. Secondary Efficacy Endpoint(s) and Analyses

Secondary efficacy endpoints will be summarized using descriptive statistics by age categories, treatment schedule and overall, unless otherwise specified.

### 8.2.1. Serum IgG Trough Levels (Total IgG)

Serum IgG Trough Levels are collected before each infusion and at the study termination visit (week 51/52) and are analyzed at a central laboratory. The following information will be summarized for each visit:

- Actual value, change from baseline and relative change from baseline
- Number and percentage of patients with target level of  $\geq 6$  g/L (8) for actual value reached/not reached

Definition of baseline is given in [Section 6.2.2.](#)

### 8.2.2. IgG subclasses levels (IgG1, IgG2, IgG3, IgG4)

IgG subclasses levels are collected before infusions 1, 5, 9 and 13 for the 28-day infusion schedule, and before infusions 1, 7, 11 and 17 for the 21-day infusion schedule and are analyzed at a central laboratory. The following information will be summarized for each visit:

- Actual value, change from baseline and relative change from baseline

Definition of baseline is given in [Section 6.2.2.](#)

### 8.2.3. Anti-tetanus toxoid antibody level (quantitative assay)

Anti-tetanus toxoid antibody levels are collected before infusions 1, 5, 9 and 13 for the 28-day infusion schedule, and before infusions 1, 7, 11 and 17 for the 21-day infusion schedule and are analyzed at a central laboratory. The following information will be summarized for each visit:

- Actual value, change from baseline and relative change from baseline

Definition of baseline is given in [Section 6.2.2.](#)

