## 6. General Aspects for Statistical Analysis

### 6.1. General Methods

- Unless otherwise specified, summaries will be presented for each treatment schedule (21-day and 28-day infusion schedule) and overall.
- Unless otherwise specified, continuous variables will be summarized using the number of observations (n), mean, standard deviation (SD), median, minimum, and maximum. Categorical variables will be summarized using number of observations (n), frequency and percentages of patients.
- All relevant patient data will be included in listings. All patients entered into the database will be included in patient data listings.
- Unscheduled assessments will not be included in summary tables unless specified otherwise, but will be included in the patient listings.

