#### 6.2.2. Baseline

For purpose of the analysis, the baseline value is defined as the last nonmissing valid observation before the first infusion. In most cases this will be the Day 1 pre-dose value. However, if the Day 1 pre-dose value is missing or was obtained after the first infusion of study drug is administered, then the most recent value obtained prior to the initiation of study drug will serve as the baseline measurement and may be measured at an unscheduled visit.

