#### 6.2.4. Relative change from baseline

Relative change = [(Post-baseline value – Value at baseline) / Value at baseline] x100

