#### 9.4.4. PK data summarization

- The mean/median value at a time point where 1 or more samples have BLQ values will be reported (in tabular or graphical fashion) even if the mean/median value is BLQ.
- Zero mean or median values will be included in summary tables.
- SD will not be displayed if more than 30% of values are missing or BLQ.

Tables of summary statistics for concentration-time data will report N (number of patients in the analysis population), n (number of actual observations) and the percentage of BLQ values relative to the total number of observations.

Following presentations of mean PK concentrations will be produced:

- Table of PK concentrations summarized by nominal time for each dosing schedule.
- Mean PK profiles in linear and log-linear scale by dosing schedule and plotted vs. nominal time relative to the start of intense sampling infusion
- Median trough concentrations vs. nominal time elapsed from the start of 1st infusion or infusion number by dosing schedule

Pharmacokinetic parameters and serum concentration data will be summarized by each dosing schedule using the following descriptive statistics:

This document is confidential.

Table 1: Concentration Summary Statistics

Variable	Summarized with:
Serum concentration at each time point	n, number and % BLQ, arithmetic mean, SD, coefficient of variance (CV) %, minimum, median and maximum
Continuous PK parameters ( $C_{max}$ , AUCs, ...)	n, arithmetic mean, SD, CV%, minimum, median, maximum, geometric mean and geometric CV%
Categorical PK parameters ( $T_{max}$ )	n, minimum, Q1, median, Q3 and maximum
Semi-continuous PK parameters ( $T_{1/2}$ , $K_{el}$ )	n, arithmetic mean, SD, CV%, minimum, median, maximum

CV% = SD/mean in %.

%BLQ = 100 \* (total number of patients who have BLQ values/total number of patients within each dose level at each time point)

Table 2: Precision of PK Data Reporting

Statistics	Degree of Precision
Minimum, Maximum	3 significant digits or as needed based on actual measured values (for example PK concentrations)
Mean (arithmetic and geometric), Median, Q1, Q3	4 significant digits or as needed based on actual measured values (for example PK concentrations)
SD	5 significant digits or as needed based on actual measured values (for example PK concentrations)
CV% and Geometric CV%	1 decimal place or as needed based on actual measured values (for example PK concentrations)

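### The mean percent change planned for IgG and antibody levels is biased upward when nothing has changed; a geometric mean ratio to baseline would correct this at little cost

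*SAP*

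**What the plan says.** The plan for these endpoints has to be assembled from several parts of the SAP.

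- Sections 8.2.1 to 8.2.6 cover total IgG troughs, the four IgG subclasses, and antibodies to tetanus toxoid, pneumococcal polysaccharide, measles and *Haemophilus influenzae* type b. Each asks for the same quantities by visit: "Actual value, change from baseline and relative change from baseline". Section 8.2.1 adds the number of patients reaching the trough target.
- Section 6.2.4 defines the percent change per patient: "Relative change = [(Post-baseline value – Value at baseline) / Value at baseline] x100".
- Section 6.2.2 makes the denominator one measurement: "the baseline value is defined as the last nonmissing valid observation before the first infusion".
- Section 6.1 sets the statistics: "Unless otherwise specified, continuous variables will be summarized using the number of observations (n), mean, standard deviation (SD), median, minimum, and maximum".
- Section 8.2 does not override this: "Secondary efficacy endpoints will be summarized using descriptive statistics by age categories, treatment schedule and overall, unless otherwise specified".

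The arithmetic mean of individual percent changes is therefore planned. So are its median, the mean and median absolute change, and the actual values. The visible text of 8.2.1 to 8.2.6 plans no log transformation, geometric mean or geometric mean ratio. Geometric statistics appear in Table 1 of section 9.4.4, for continuous PK parameters such as Cmax and the AUCs: "n, arithmetic mean, SD, CV%, minimum, median, maximum, geometric mean and geometric CV". The row of that table for serum concentrations uses arithmetic statistics only.

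The SAP revision history (version 4.0) records that relative change was added to these sections in response to FDA comments.

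**The concern.** A percent change divides by a baseline that carries its own measurement and biological noise. A baseline that is low by chance inflates the ratio more than one that is high by chance deflates it. Averaging such ratios over patients gives a positive figure even when levels are stable.

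The trial has one arm, and every patient enters on commercial IVIg (SAP 3.5.1, criterion 4). Baseline therefore reflects the earlier product, and the direction of the error flatters the study product. What is at stake is a descriptive row in the secondary efficacy tables. A reader who takes the mean percent change at face value could see a small gain where there is none, or no change where levels have fallen slightly.

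**Working it through.** The documents give no figure for this bias, so there is none to reproduce.

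**Inputs.** Percent change is as defined in SAP 6.2.4, with a single baseline value (6.2.2) and an arithmetic mean over patients (6.1). The illustration uses 40 patients, the evaluable number in SAP 3.6. The within-patient CV is not given in the documents; values from 10% to 50% are assumed.

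**Step 1, direction.** Let X be baseline and Y the visit value, positive and exchangeable within a patient (no true change). Since Y/X + X/Y ≥ 2 always, and E[Y/X] = E[X/Y], it follows that E[Y/X] ≥ 1, with equality only if X = Y. Example: one patient goes from 1 to 2 and another from 2 to 1. The percent changes are +100 and −50, with mean +25%. The mean absolute change is 0 and the geometric mean ratio is √(2 × 0.5) = 1.00.

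**Step 2, size.** With log-normal errors and the same CV on each occasion, the log-scale variance per occasion is ln(1 + CV²). If the errors are independent, Var(log Y/X) = 2 ln(1 + CV²), and

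E[Y/X] − 1 = exp{½ × 2 ln(1 + CV²)} − 1 = CV².

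This does not depend on the number of patients, so a larger sample does not remove it.

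**Step 3, simulation.** 100,000 trials of 40 patients, no true change, independent errors:

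| Assumed CV | Expected mean % change (CV²) | Trials with mean above 0 | Average median % change | Average geometric mean ratio |
|---|---|---|---|---|
| 10% | +1.0% | 67% | +0.1% | 1.000 |
| 15% | +2.3% | 74% | +0.1% | 1.001 |
| 20% | +4.0% | 80% | +0.2% | 1.001 |
| 30% | +9.0% | 89% | +0.3% | 1.002 |
| 50% | +25.0% | 97% | +0.9% | 1.006 |

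An unbiased summary would be above zero in about 50% of trials. The simulated mean percent changes agree with CV² to within 0.1 percentage points.

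**Step 4, what could be hidden.** The expected mean percent change is zero when the true ratio is 1/(1 + CV²). That is 1/1.0225 = 0.978 at CV 15%, 1/1.09 = 0.917 at 30%, and 1/1.25 = 0.80 at 50%. True falls of about 2%, 8% and 20% would then show as no change on average.

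**Step 5, correlated errors.** With log-scale correlation ρ between baseline and visit errors, the bias becomes (1 + CV²)^(1−ρ) − 1. At CV 30% and ρ = 0.5 this is √1.09 − 1 = 4.4%, against 9% when ρ = 0.

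**The case against.** The strongest reply is that the tables already contain figures without this fault. Under no true change the mean absolute change has expectation zero, and the median percent change stays within 1% of zero at every CV tabulated above. Both are planned for the same visits. This stands, and it limits the point to one statistic among several.

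A reader might infer that the trial's comparison of the study product with previous IVIg rests on these percent changes. The documents do not support that. The stated pre-study comparison concerns total IgG troughs only (Protocol 3.1, SAP 3.1.3). SAP 9.6 carries it out descriptively with box plots and does not name percent change. The antibody and subclass endpoints are defined as levels before given infusions, and no test or success rule uses them.

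A reader might also infer that the SAP contradicts itself by using geometric means for PK parameters and not here. Table 1 in SAP 9.4.4 treats serum concentrations arithmetically too, so the choice is consistent for concentrations. It shows only that geometric statistics are already part of the planned output.

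Three further replies stand:

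- The CVs are assumed. At 10% to 15%, as might apply to total IgG, the bias is only 1% to 2%.
- Relative change was added to address FDA comments, which is a reason to keep the row. It is not a reason to lead with its arithmetic mean.
- The text just before SAP 9.6 is redacted and the table shells are not supplied. A geometric summary may exist there, so its absence can be stated only for the visible text.

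**Conclusion.** The point holds as a modest improvement to descriptive tables. The arithmetic mean of individual percent changes in SAP 8.2.1 to 8.2.6 is biased upward under no change by about CV². That is +1% to +2% at CV 10% to 15%, +9% at 30% and +25% at 50%. These sizes rest on assumed CVs, log-normal within-patient variation and independent errors at baseline and visit. Positive correlation reduces them, as step 5 shows. The case is weakest for total IgG and stronger for specific antibodies and subclasses if, as seems plausible, these vary more within a patient.

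It does not follow that the SAP reports antibody levels only in a biased way, or that any efficacy conclusion is at risk. The primary analysis does not use these data.

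**What to change.** In SAP 8.2.1 to 8.2.6, and at least for the specific antibodies and subclasses:

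1. Add by visit the geometric mean and the geometric mean ratio to baseline with a 95% CI, obtained by back-transforming the mean log ratio and its limits.
2. Name that ratio, or the already planned median percent change, as the lead summary of relative change in place of the arithmetic mean. The median needs no new row, but it has no planned interval and, on the log scale, about a 25% larger standard error than the mean log ratio.
3. Keep the planned rows, including the arithmetic mean, for reference.
4. State that the quantification-limit rule of SAP 9.4.2 also applies to these endpoints, including baseline values. That rule stands in the PK section and does not name anti-measles antibody (8.2.5). A baseline set to half the limit can produce a very large percent change, so the number of such baselines should be shown.

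The cost is a few extra table rows and a sentence on quantification limits. No new data are needed.

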### 8.2.4. Anti-pneumococcal capsular polysaccharide antibody level (quantitative assay)

Anti-pneumococcal capsular polysaccharide antibody levels are collected before infusions 1, 5, 9 and 13 for the 28-day infusion schedule, and before infusions 1, 7, 11 and 17 for the 21-day infusion schedule and are analyzed at a central laboratory. The following information will be summarized for each visit:

- Actual value, change from baseline and relative change from baseline

Definition of baseline is given in [Section 6.2.2.](#)

### 8.2.5. Anti-measles antibody level (quantitative assay)

Anti-measles antibody levels are collected before infusions 1, 5, 9 and 13 for the 28-day infusion schedule, and before infusions 1, 7, 11 and 17 for the 21-day infusion schedule and are analyzed at a central laboratory. The following information will be summarized for each visit:

- Actual value, change from baseline and relative change from baseline

This document is confidential.

Definition of baseline is given in [Section 6.2.2](#).

8.2.6. Anti-Hemophilus influenza type b antibody level (quantitative assay)

Anti-hemophilus influenza type b antibody levels are collected before infusions 1, 5, 9 and 13 for the 28-day infusion schedule, and before infusions 1, 7, 11 and 17 for the 21-day infusion schedule and are analyzed at a central laboratory. The following information will be summarized for each visit:

- Actual value, change from baseline and relative change from baseline

Definition of baseline is given in [Section 6.2.2](#).

8.2.7. Any infection other than acute serious bacterial infections

The following information will be summarized for infections between day 1 and week 51/52:

- Estimate of mean and SD of the incidence rate by the simple estimator.
- Duration of the considered infection(s)
- The estimate and 1-sided 99% upper confidence limit using Poisson model.

The length of the observation period after the start of treatment per patient will be used as offset in the Poisson model. The unit of measurements of time is years.

Definition of incidence rate is given in [Section 8.1.1](#).

Computation of the estimate and 1-sided 99% upper confidence limit using Poisson model is given in [Section 8.1.2](#).

Computation of the simple estimator is given in [Section 8.1.3](#).

Definition of duration of infection is given in [Section 6.2.8](#).

8.2.8. Fever episodes

The following information will be summarized for fever episodes between day 1 and week 51/52:

- Estimate of mean and SD of the incidence rate by the simple estimator.
- Duration of fever
- The estimate and 1-sided 99% upper confidence limit using Poisson model.

The length of the observation period after the start of treatment per patient will be used as offset in the Poisson model. The unit of measurements of time is years.

Definition of incidence rate is given in [Section 8.1.1](#).

Computation of the estimate and 1-sided 99% upper confidence limit using Poisson model is given in [Section 8.1.2](#).

Computation of the simple estimator is given in [Section 8.1.3](#).

Definition of duration of fever is given in [Section 6.2.10](#).

8.2.9. Hospitalization/ Hospitalization due to Infection

The following information will be summarized for hospitalizations between day 1 and week 51/52:

- Total days of hospitalization (any cause)

This document is confidential.

- Total days of hospitalization (any infection)

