### 4.2. Secondary Efficacy Endpoints

1. Serum IgG trough levels before each infusion of KIG10 and at the study termination visit (week 51/52).
2. IgG subclasses levels (IgG1, IgG2, IgG3, IgG4) before infusions 1, 5, 9 and 13 for the 28-day infusion schedule, and before infusions 1, 7, 11 and 17 for the 21-day infusion schedule.
3. Frequency of patients with total IgG below 6 g/L criteria.
4. Anti-tetanus toxoid antibody level (quantitative assay) before infusions 1, 5, 9 and 13 for the 28-day infusion schedule and before infusions 1, 7, 11 and 17 for the 21-day infusion schedule.
5. Anti-pneumococcal capsular polysaccharide antibody level (quantitative assay) before infusions 1, 5, 9 and 13 for the 28-day infusion schedule and before infusions 1, 7, 11 and 17 for the 21-day infusion schedule.
6. Anti-measles antibody level (quantitative assay) before infusions 1, 5, 9 and 13 for the 28-day infusion schedule and before infusions 1, 7, 11 and 17 for the 21-day infusion schedule.
7. Anti-Hemophilus influenza type b antibody level (quantitative assay) before infusions 1, 5, 9 and 13 for the 28-day infusion schedule and before infusions 1, 7, 11 and 17 for the 21-day infusion schedule.
8. Incidence rate (i.e., the mean number per patient-year) of any infection other than acute serious bacterial infections from day 1 to week 51/52.
9. Duration of any infection other than acute serious bacterial infections from day 1 to week 51/52.
10. Incidence rate (i.e. the mean number per patient-year) of fever episodes, from day 1 to week 51/52.
11. Duration of fever episodes, from day 1 to week 51/52.
12. Overall hospitalization days from day 1 to week 51/52.
13. Days of hospitalizations due to infection from day 1 to week 51/52.
14. Incidence rate (i.e. the mean number per patient-year) of patients on antibiotics for the treatment of any kind of infection from day 1 to week 51/52.
15. Duration of patients on antibiotics for the treatment of any kind of infection from day 1 to week 51/52.
16. Days of missed work/school/other major activities due to infections from day 1 to week 51/52.

This document is confidential.

17. PedsQL™ score at baseline, week 24 (infusion 7 for the 28-day schedule and infusion 9 for the 21-day schedule), and at the study termination visit.

CCI

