#### 8.2.11. Days of missed work/school/other major activities due to infections

The following information will be summarized for missed work/school/other major activities due to infections between day 1 and week 51/52:

- Total days of missed work/school/other major activities due to infections

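### Hospital days and missed work, school or activity days are summarized only as totals, with no adjustment for observation time, so they fall as follow-up is lost

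*SAP*

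**What the plan says.** SAP 8.2.9 lists two summaries: "Total days of hospitalization (any cause" and "Total days of hospitalization (any infection". SAP 8.2.11 lists one: "Total days of missed work/school/other major activities due to infections". Neither section gives a rate, an offset or a patient-year denominator, and no redaction is visible in either.

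The neighbouring sections treat event counts differently. SAP 8.2.7, 8.2.8 and 8.2.10 each ask for "Estimate of mean and SD of the incidence rate by the simple estimator" and add a Poisson estimate, for which "The length of the observation period after the start of treatment per patient will be used as offset in the Poisson model". The denominator of the simple estimator is set out in SAP 8.1.3: "The number of patient years will be calculated by summing the total patient days and dividing by 365".

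The rule governing all these tables is in SAP 8.2: "Secondary efficacy endpoints will be summarized using descriptive statistics by age categories, treatment schedule and overall, unless otherwise specified". The day totals will therefore also be broken down by age and schedule.

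The SAP matches the protocol here. SAP 4.2 defines the endpoint as "Overall hospitalization days from day 1 to week 51/52", and Protocol 10.4.1 likewise defines it as days.

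**The concern.** A total of observed days counts unobserved time as zero days. Anyone who received one dose is in the Full Analysis Set (SAP 5.2), so a patient who leaves early stays in the table with a truncated count. SAP 6.3 replaces no missing data unless a section says so, and 8.2.9 and 8.2.11 say nothing; the multiple imputation in SAP 6.3.1 is for the primary endpoint.

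The counts come from the diary (Protocol 8.1.4 and 8.1.6.1), which at withdrawal is collected, if available, only up to the day of withdrawal (Protocol 4.8). Protocol 10.7 regards missing data as harmless for the primary analysis because a leaver contributes less person-time. That protection does not extend to a raw total.

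The wording allows two readings, and neither adjusts for time. A grand total also depends on group size, so it cannot be compared across the planned schedule and age breakdowns. A per-patient total averaged over the set is low whenever follow-up is incomplete. At stake is the interpretation of three secondary burden endpoints.

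**Working it through.** **Inputs from the documents.** SAP 3.6: 40 evaluable patients, 10% dropout, 10% screening failures, about 50 screened; serious bacterial infection rate 0.49 against 1.0 per year, 1-sided alpha 0.01, 90% power. SAP 6.4: follow-up to week 51 (21-day schedule) or week 52 (28-day schedule). The documents state no expected figure for hospital or missed days.

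**Reproducing the plan's figures.** With 40 patient-years, the exact Poisson test rejects at 25 or fewer events, since P(X ≤ 25 | mean 40) = 0.0076 and P(X ≤ 26 | mean 40) = 0.0123. Power is P(X ≤ 25 | mean 40 × 0.49 = 19.6) = 0.905, in line with the stated 90%. Inflation gives 40 / (0.9 × 0.9) = 49.4, rounded up to 50. The 10% dropout is therefore a genuine planning input and is used below.

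**Shortfall of a raw total.** Let d be the dropout share and f the mean fraction of planned follow-up that leavers complete (f is an assumption). With a constant day rate,

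shortfall = 1 − [(1 − d) + d × f] = d × (1 − f).

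| d | f = 0.75 | f = 0.5 | f = 0 |
|---|---|---|---|
| 10% (plan) | 2.5% | 5% | 10% |
| 20% (assumed) | 5% | 10% | 20% |

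The same percentages apply to the mean total per patient in the Full Analysis Set.

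**Schedules.** 51/52 = 0.981, so the 21-day group has 1.9% less planned observation time.

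**What a patient-year rate corrects.** With a constant day rate, observed days and observed person-time shrink by the same factor, so the ratio to the true rate is 1.00.

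Now suppose leavers have twice the day rate of the others (assumption; d = 10%, f = 0.5, others' rate set to 1):

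- Full-follow-up days per planned patient-year: 0.9 × 1 + 0.1 × 2 = 1.10.
- Observed days: 0.9 × 1 + 0.1 × 0.5 × 2 = 1.00, so the raw total is 1 − 1.00/1.10 = 9.1% low.
- Observed person-time: 0.9 + 0.1 × 0.5 = 0.95. The rate is 1.00/0.95 = 1.053, and 1.053/1.10 = 0.957, so it is 4.3% low.

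In this example the rate removes about half of the error.

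**The case against.** The strongest reply is that the plan is coherent as it stands: event counts become rates, and day quantities do not. The durations of infections, fever and antibiotic use in SAP 8.2.7, 8.2.8 and 8.2.10 have no observation-time denominator either. The protocol itself defines the three endpoints as days. The SAP revision history records that Poisson estimates were added to 8.2.7, 8.2.8 and 8.2.10 after regulatory comments, and mentions no such addition to 8.2.9 or 8.2.11; that suggests a deliberate distinction without proving one. This stands. A reader might infer that every other infection endpoint is per patient-year, or that the SAP departs from the protocol. The documents support neither: the contrast is with the incidence-rate items only.

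Second, a total of observed days correctly describes what was observed. It is low only as an estimate of full-follow-up burden. This also stands. A reader might infer a distorted comparison with a historical yearly burden, because the study is called historically controlled. No threshold, test or historical comparison is planned for these endpoints; the benchmark of 1.0 per year belongs to serious bacterial infections.

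Third, Protocol 4.8 says that withdrawing patients will be asked to remain in safety follow-up for the duration of the study, so leaving treatment need not end observation. Where that succeeds, the loss shrinks. It is a request, however, and the sample-size section still allows for 10% dropout.

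Finally, the data will be listed by patient and the table shells are not in the documents, so a reader with all outputs could derive a rate. The SAP text nevertheless specifies none.

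**Conclusion.** The point holds as a low-cost reporting improvement. The three day totals are not adjusted for observation time, and nothing else in the plan supplies the adjustment. At the planned 10% dropout they understate full-follow-up days by about 5%, with a range of 2.5% to 10% set by the assumed time of leaving, under a constant day rate. The schedules differ by a further 1.9% in planned observation time. The endpoints are descriptive, and the primary efficacy claim is unaffected.

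Two stronger readings should be resisted. One is to treat the up to 12 pediatric patients (Protocol 5) as a single subgroup and quote 1/12, about 8%, for one immediate withdrawal. SAP 6.6.1 splits these patients into ages 2 to 11 and 12 to 17, so that figure matches no planned category. The other is that dropout is caused by infection and that a patient-year rate would cure it. The documents do not establish the cause, and the working shows that the rate would correct such dropout only in part.

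**What to change.** In SAP 8.2.9 and 8.2.11, add days per patient-year for each of the three endpoints: total days divided by total patient-years, with patient-years as in SAP 8.1.3, overall, by treatment schedule and by age category. Keep the totals alongside, so that the protocol endpoint is still reported as defined. Note in the text that the rate adjusts for lost time and not fully for illness-related dropout.

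A patient-level bootstrap interval is optional and best limited to the overall estimate; in very small age groups with mostly zero days it would be unstable.

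The cost is one sentence in each of the two sections and one extra table row per endpoint. The patient-years are already needed, in the same breakdowns, for the rates in SAP 8.2.7, 8.2.8 and 8.2.10. No additional data collection is required.
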